136 **7.3. Study Procedures/Research Interventions.** The principal investigator will brief ED physicians on details

137 of this study by email (Appendix D). ED physicians who identify that a patient will require an ultrasound will
138 page the ultrasound team as part of standard of care. At that time, the AI (ultrasonographer) will ask subject if
139 he/she would like to participate in a research study involving patient satisfaction and diagnostic bedside
140 ultrasound. If the patient agrees, the AI will provide an information sheet (Appendix C) and explain study
141 details/answer any questions. The patient will then be randomized and assigned a HUGS-X number that will be
142 placed in the comments section of the ultrasound image and given a 3-question patient survey (Appendix A)
143 related to patient satisfaction and perceptions about their provider which will be completed at the end of the
144 ultrasound procedure. The patient will be instructed not to provide any PII/PHI when he/she completes the
145 survey after the diagnostic bedside ultrasound and to hand it back to the AI when complete.

146
147 **Ultrasound and Warm or Room Temp Gel Procedures:**
148

149 The AIs will use either the warm or cold gel to complete their standard of care diagnostic ultrasound scans.
150 Subjects will be randomized to receive either warm or cold gel depending on the study packet number. The
151 study packet number will contain specific randomized instructions for the AI that provides the appropriate gel
152 numbered 1-6 to utilize and the 3-question patient survey and 1 question provider survey.

153 Patients and providers will be blinded to the intervention meaning both the AI and the patient will be
154 unaware of different gel temperatures being utilized until the moment it is used on the patient's ultrasound
155 area.

156 The provider (AI) will be blinded to the intervention used in two ways. The first being that six ultrasound gel
157 warmers, labeled #1-6, will be set up at a station, and the warmers will have been randomly set-up as far
158 which are actually turned on or not by the PI. The AI will not know which are turned on because the indicator
159 lights will be covered with black tape. Additionally, the AI will use heat-resistant gloves to hold the
160 ultrasound gel bottle as described in section 7.2.2. At the end of the subject's bedside ultrasound, the

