161 physician completing the ultrasound will hand the patient a satisfaction survey utilizing visual analog scales.
162 As an additional measure to test our blinding measure, the AI will complete the one question survey to test
163 whether he or she was aware of the warm or room-temperature gel temperature.

164 Both surveys will be collected and stored in a locked box in C-Pod of the Emergency Department until
165 results can be entered in to the electronic spreadsheet (HUGS DataTracker Data Collection Spreadsheet,
166 Appendix G)

167
168 **The Ultrasound Image Rating:**
169

170 Ultrasound image rating is conducted weekly by the SAMMC ED/Ultrasound Quality Assurance Team on a
171 weekly basis. These meetings are already a standard practice in our department to review every ultrasound
172 obtained in the department as a way to obtain feedback from all clinicians about the quality of their
173 ultrasound studies. Their standard metric for evaluation is a 5-point Likert-type scale. During this QA review,
174 scores related to images that have a HUGS ID in the comments area will be written down and provided to
175 the PI. Their standard metric for evaluation is a 5-point Likert-type scale.

176 Table I: Summary of Study Activity/Interventions
177

Assessment:	During ED Visit:	Weekly Ultrasound QA Session:
Screening	X	
Randomization	X	
Bedside Ultrasound	X	
Anonymous Patient Survey Appendix A)	X	
Provider Survey (Appendix B)	X	
Review of Ultrasound Images for Overall Quality		X

178
179 **7.3.1 Collection of Human Biological Specimens.** N/A
180

181 **7.3.1.1 Laboratory evaluations and special precautions.** N/A
182

183 **7.3.1.2 Specimen storage.** N/A
184

185 **7.3.2 Data Collection.** Subject specific data (patient age, gender, and their satisfaction scores) will all be
186 written on the anonymous survey (Appendix A). The primary outcome will be a visual analogue scale, i.e.
187 continuous variable. By collecting a variable with greater data density than a conventional Likert scale (e.g.,
188 ordinal data), this will enable us to use more powerful statistical techniques in analyzing our data so minimizing
189 the possibility of a type II (beta) error. We will further evaluate our secondary outcomes with Likert-type scales
190 to minimize millimeter differences between patient scores. Finally, we will use binary data to evaluate whether
191 patients were overall satisfied with their visit.
192

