193 Primary Outcome #1a: Overall, how satisfied are you with the experience of having a bedside ultrasound today?
194• Ranges from “Least” to “Most” on 10cm VAS (continuous data)
195

196 Primary Outcome #1b: Overall, are you satisfied with the care you received today in the Emergency
197 Department?
198• “Yes” or “No” (binary data)
199

200 Secondary Outcome #1: Overall, how professional was the physician who did your bedside ultrasound?
201• Ranges from “Least” (1) to “Most” (5) on 5-point Likert-type scale (ordinal data)
202

203 The subject survey form will not contain any PHI/PII. Completed packets will be taken to the locked bin in C-Pod
204 of the Emergency Department. We will also store the completed provider surveys in the same container to allow
205 for further evaluation of provider answers regarding which type of gel they believe they used and if the blinding
206 method imposed by the PI prevented the provider from knowing which gel they utilized.
207

208 New study packets will be kept in a separate designated bin within the Emergency Department, next to the
209 ultrasound gel warmers, so that associate investigators may access all required materials while working in the
210 department. The PI or available AI will pick up completed packets weekly and will either log the data
211 immediately or store them in the designated locked bin in the ultrasound team room until they can be entered
212 into the HUGS DataTracker spreadsheet.
213

214 Subject bedside ultrasounds, like any clinical ultrasound done in our hospital, are uploaded automatically to the
215 IMPAX system. Each week, the SAMMC ED/Ultrasound Quality Assurance Team reviews all bedside
216 ultrasounds for quality assurance purposes. Their standard metric for evaluation is a 5-point Likert-type scale.
217 This type of data is ordinal (and is the basis for secondary outcome #2). These scores will be logged by the PI or
218 available AI into an Excel Spreadsheet found on a password-protected computer behind a locked door in the
219 ultrasound team room. As all investigators are blinded to which ultrasounds were conducted with warm or cold
220 gel, there is no concern for a bias regarding the rating of quality for each ultrasound or during entering survey
221 data to the HUGS DataTracker. Upon transfer of all data to the spreadsheet, the paper surveys and hand-
222 written scores for each ultrasound will be shredded.
223

224 **7.4 Statistical Consideration**

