258 file will be deleted.

259
260 The bedside ultrasounds, which are part of routine clinical care in our department, are stored within the
261 electronic IMPAX database. All completed ultrasounds for the past week within our emergency department are
262 automatically queued for review by our ultrasonography team. This process is inherent in our system and is not
263 specially designed for this research. They will know that an ultrasound study is part of the research study as the
264 "HUGS" identifier will be seen in the comments box of the ultrasound images. Only medical providers within the
265 military healthcare system have access to these scans.

266
267 **7.5.1 Certificate of Confidentiality.** N/A

268
269 **8.0 RISKS/BENEFITS ASSESSMENT**

270
271 **8.1 Risks.** There are minimal risks for this study. Although this survey is anonymous and cannot be tracked
272 to specific individuals, there is a small risk of inadvertent breach of confidentiality. Participants will not be
273 identified and will be reminded not to add identifiers to their survey documents. For the ultrasound images
274 on IMPAX, only military providers within the military healthcare system have access. Risk of a confidentiality
275 risk is similar to the normal, daily risk of breach in our healthcare system.

276
277 • There is also the risk of brief discomfort to subjects related to the gel temperature. Medical devices heat the
278 gel to a maximum temperature of 104 degrees. Injuries from gel at this temperature or at room temperature
279 are very unlikely to occur.
280 • Although there is a minimal risk of gel being contaminated with microbiota, we will further mitigate the risk by
281 excluding patients with broken skin in the area of where an ultrasound probe would be placed onto the skin.

282
283 **8.2 Potential Benefits.** There may be direct benefits to participants. Subjects enrolled in the warm gel
284 group may benefit from a more comfortable ultrasound.

285
286 **9.0 ADVERSE EVENTS, UNANTICIPATED PROBLEMS, AND DEVIATIONS**

287
288 **9.1** An adverse event in this study would be either a burn to the patient, infection, or a breach of confidentiality.
289 These are considered rare but serious, as described above. Adverse events during the study would be
290 documented by the ultrasonographer or another member of the research team and reported by the PI to the IRB
291 as required.

292

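### Gel-temperature discomfort is a named risk in 8.1, but 9.1's adverse-event definition excludes it and no described form item records it, so it cannot be tabulated by arm

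*Combined protocol and SAP*

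**What the plan says.** Section 8.1 names a physical effect of the intervention: "There is also the risk of brief discomfort to subjects related to the gel temperature". It also treats injury from the gel and contamination of the gel as unlikely or minimal risks.

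Section 9.1 reads: "An adverse event in this study would be either a burn to the patient, infection, or a breach of confidentiality". It calls these events uncommon but serious and refers back to the preceding text. They are to be "documented by the ultrasonographer or another member of the research team and reported by the PI to the IRB". No form is named, and nothing says whether patients are asked.

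Section 7.3 describes each study packet as holding instructions on which gel to use, "numbered 1-6 to utilize and the 3-question patient survey and 1 question provider survey". On the patient form, 7.3.2 says: "Subject specific data (patient age, gender, and their satisfaction scores) will all be" written on the anonymous survey. Its three questions are:

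- "Overall, how satisfied are you with the experience of having a bedside ultrasound today" (10 cm VAS);
- overall satisfaction with care in the Emergency Department (yes/no), introduced as "Primary Outcome #1b: Overall, are you satisfied with the care you received today in the Emergency";
- "Overall, how professional was the physician who did your bedside ultrasound" (five-point scale).

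The one provider question asks whether the associate investigator (AI) doing the scan was aware of the gel temperature.

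**The concern.** The trial manipulates one thing, the temperature of the gel. The plan expects that temperature may cause discomfort, yet it provides nowhere to write discomfort down. A safety report that followed the plan exactly could show no events even if several patients had said that the gel was painfully hot.

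Two things are at stake. The first is safety information: a complaint of heat is milder than a burn and may come before one, so it is worth collecting while recruitment is under way. The second is reporting. The rationale in section 4 is comfort, and 8.2 offers a more comfortable scan as a possible benefit of warm gel. Without a record of complaints, the trial cannot say how well either gel was tolerated.

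**Working it through.** The point rests mainly on reading the sections against each other.

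**1. Risk against definition.** 8.1 lists discomfort from gel temperature. 9.1 defines an adverse event as one of three things, and discomfort is not among them. The wording is a closed list, not a set of examples.

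**2. Definition against forms.** The described data items are age, gender, three patient questions and one provider question. None asks about heat, cold or pain. The VAS asks about the whole ultrasound experience, so a low score could reflect discomfort or something else.

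**3. The other reporting route.** 9.2 requires 48-hour reporting of problems that pose risk to subjects and were not anticipated. No burn is needed. But 8.1 already anticipates brief discomfort, so an ordinary complaint arguably falls outside 9.2 as well as 9.1.

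**4. What the operator can observe.** Under 7.3 the warmers' indicator lights are taped over and the AI holds the bottle in a heat-resistant glove. No check of gel temperature is described. The patient's reaction is therefore the main described source of information about a gel that is too hot.

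**5. Later reconstruction.** Under 7.5, surveys cannot be linked to charts, paper is shredded once entered, and the data are destroyed after analysis. Under 10.0, the packet of a subject who withdraws before handing in the survey is shredded if it has been written on. A complaint not recorded at the time is unlikely to be recoverable.

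**6. Burn counts as a substitute.** Inputs from 7.4.1: 114 required and 124 enrolled, in equal groups, so 114/2 = 57 to 124/2 = 62 warm-gel subjects. With no burns among n subjects, the exact one-sided 95% upper limit is 1 − 0.05^(1/n):

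- n = 57: 1 − 0.05^(1/57) = 0.051, or 5.1%;
- n = 62: 1 − 0.05^(1/62) = 0.047, or 4.7%.

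An empty 9.1 listing would thus say little about thermal tolerability. The plan states no safety figure to reproduce.

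**7. Two related inconsistencies.** 9.1 calls its events serious by reference to earlier text, but 8.1 describes none of them as serious. Separately, 8.1 gives a maximum gel temperature of 104 degrees, while 7.2.2 lists warmer settings of 97, 102 and 109 Fahrenheit and says all warmers are on Medium (102). The figure of 104 matches none of the listed settings. These passages must be reconciled.

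**The case against.** A reader might infer that an overheated gel would be noticed only once it burned someone. The documents do not support that. Patients with altered mental status, or whose primary language is not English, are excluded, and the AI is present when the gel is applied, so a complaint would normally be heard. A suspected warmer fault could be reported under 9.2 without a burn.

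Nor does it follow that the PI would have nothing to act on. The packet tells the AI which numbered gel is in use, so the number can be passed on with a complaint. All warmers share one setting, and only their on/off status is hidden.

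It would also be wrong to put a number on lost complaints, or on subjects exposed to a faulty warmer. The documents give no complaint rate and no fault rate, and they do not say that the six gels are used equally.

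Three further objections carry some weight. Tolerability is not among the three hypotheses. The VAS will pick up some unpleasantness, if non-specifically. And the contents of Appendices A, B and G are known only from the body text.

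What stands against all this is narrower. Hearing a complaint is not recording it: nothing requires anyone to write it down, no trigger for passing it on is defined, and nothing described would allow a count by arm.

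**Conclusion.** The point holds in a limited form. Discomfort from gel temperature is a named risk that lies outside the adverse-event definition and outside every described data item. Complaints short of a burn are therefore not systematically recorded, have no defined reporting trigger and cannot be tabulated by arm.

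This is a gap in recording and reporting. It is not evidence that patients are unprotected or that faults would go unnoticed. It does not touch the primary comparison. Its size in events cannot be stated. The one available figure is that burn counts alone would leave an upper limit of about 5% in the warm arm.

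The conclusion assumes that the appendix forms match their descriptions in 7.3 and 7.3.2. If Appendix A, B or G already carries a discomfort item, what remains is to bring 9.1 and the planned tabulation into line with it.

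**What to change.** - **Provider survey (Appendix B).** After the blinding question, add separate tick-boxes for a spontaneous complaint of too hot, too cold or pain. A single yes/no box would lose the direction of the complaint. Identify the form by packet number only, which the PI can link to the gel. Writing the gel number beside a heat complaint could show other AIs which warmer is on.
- **Section 9.1.** List these complaints as non-serious recorded events, passed to the PI and tabulated by arm. State how they relate to 9.2, including when a complaint counts as an unanticipated problem.
- **Section 10.0.** Say what happens to this item when a subject withdraws, since the packet may be shredded.
- **Reconcile** the description of events as serious in 9.1 with 8.1, and the 104-degree maximum in 8.1 with the settings in 7.2.2.

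The cost is one short item on a form already completed for each subject, and a few sentences of protocol text. The downside is that a heat complaint partly reveals warmer status to whoever logs the form. Section 7.3.2 lets the PI or any available AI log data, so this item should be reserved for the PI, who under 7.3 already arranges which warmers are on. Placing the boxes after the blinding question keeps them from prompting the answer to it.
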